#### *Mepolizumab as a treatment for chronic cough in eosinophilic airways diseases*

Mepolizumab is a humanised monoclonal antibody against IL-5, which is currently licensed for treatment in patients with severe uncontrolled exacerbations. Interleukin-5 is a key cytokine controlling eosinophil growth, differentiation, recruitment, activation and survival (25-27). Treatment with mepolizumab results in a reduction in serum eosinophils and sputum eosinophils (28, 29). The main clinical benefits are in the reduction in exacerbations requiring treatment bursts of oral corticosteroids (OCS) and/or hospitalisations by approximately 50-60% (29, 30). There have been no studies which have recruited patients with chronic cough or assessed objective cough frequency as a study outcome with anti-IL5 therapy.

Therefore, the aim of this study is to evaluate the effectiveness of mepolizumab for the treatment of chronic cough in patients with eosinophilic airways disease, including both asthma and NAEB.

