## **2. Hypothesis**

We hypothesise that in patients with asthma and NAEB, eosinophils are involved in sensitising airway nerves and thereby increasing spontaneous objective coughs. We therefore predict that treatment with mepolizumab will reduce airway eosinophilia in patients with chronic cough due to eosinophilic asthma and NAEB, thereby causing a reduction in objective cough frequency.

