#### **Secondary Objectives:**

1. To determine the effects of mepolizumab on:

- i. Awake /Night-time cough frequency
- ii. Intensity of irritant sensations
- iii. Quality of life
- iv. Airway hyper-responsiveness
- v. Inflammatory cells

All the above secondary objectives will also be analysed based on disease group, i.e., asthma and NAEB.

[figure not shown]
2. The relationship between change in cough frequency and change in eosinophils

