### 9. Statistical Plan

#### 9.1. Sample Size Estimation

It is assumed that 60 subjects will be screened to randomize 30 subjects, and 15 will be randomized to complete each treatment arm in 1:1 ratio. This is a proof-of-concept study investigating the effectiveness of mepolizumab on objective cough rates in patients with

eosinophilic asthma or NAEB. As such, no formal power calculation can be currently performed. The sample size is therefore based on previous similar pilot studies using cough monitoring as an endpoint (36, 37).

With 15 patients per arm, this study will have 80% power with an alpha of 5% to detect an estimated 20% greater reduction in 24hr cough frequency compared with the placebo arm, assuming a log standard deviation of 0.60. A clinically relevant reduction in cough frequency of 20% was established following a recent phase 3 studies of gefapixant in refractory chronic cough which showed a 20% reduction over placebo as significant (38). The data from this study will be used to estimate the sample size required for any future multi-centre studies.

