#### *9.2.3. Secondary Endpoint*

Comparison of cough frequency, LCQ, mBorg, sputum and blood eosinophilia, will be performed using the same statistical approach as for the primary outcome including data after week 8 and week 14 of intervention. The proportion of subjects with a reduction in cough frequency more than 30% in the mepolizumab and placebo groups will be analysed using a chi-squared test.

The effect of intervention on changes in inflammatory cells in blood and sputum and methacholine PC20 will be compared to baseline measurements in the mepolizumab/placebo group. This will be analysed using either an independent t-test or Mann-Whitney test depending on the normality of data.

Changes in objective cough frequency will be correlated with changes in serum and sputum eosinophilia and all subjective patient reported outcomes.

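### Section 9.2.3 correlates change in cough with change in eosinophils without mentioning treatment arm; an arm-adjusted estimate should be shown beside the pooled one

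*Combined protocol and SAP*

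**What the plan says.** The second secondary objective in section 4 is "The relationship between change in cough frequency and change in eosinophils". The analysis that serves it is one sentence in section 9.2.3: "Changes in objective cough frequency will be correlated with changes in serum and sputum eosinophilia and all subjective patient reported outcomes". That sentence names no coefficient, time point, analysis set or treatment of arm.

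The only subgrouping attached to the secondary objectives is by disease: "All the above secondary objectives will also be analysed based on disease group, i.e., asthma and NAEB". It stands under objective 1 and does not concern treatment arm. Elsewhere in 9.2.3, the responder analysis and the comparison of inflammatory cells and PC20 both name the mepolizumab and placebo groups; the correlation sentence does not. Nothing else in section 9 supplies an arm-adjusted or mediation model.

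Two other statements matter here. Section 2 hypothesises that "eosinophils are involved in sensitising airway nerves and thereby increasing spontaneous objective coughs". The background in section 1.2 states that "Treatment with mepolizumab results in a reduction in serum eosinophils and sputum eosinophils", without giving a size.

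**The concern.** If the drug lowers eosinophils, change in eosinophils partly indicates which arm a participant was in. If the mepolizumab arm also coughs less, for whatever reason, the two arms form two clouds of points displaced on both axes. A single correlation through both clouds is then positive even when there is no association inside either one.

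This correlation is the only planned analysis that links eosinophils to cough at participant level. A positive result would naturally be set against the hypothesis in section 2, at the p<0.05 threshold of section 9.2.1. Under the pooled reading, part or all of that result could simply repeat the treatment comparison.

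**Working it through.** The plan gives no figure for the correlation, so there is none to reproduce. The inputs for cough come from section 9.1.

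**Inputs**
- 15 per arm, 1:1 allocation (sections 9.1 and 6.2).
- Cough effect: the trial is sized "to detect an estimated 20% greater reduction in 24hr cough frequency compared with the placebo arm", a ratio of 0.80. Effects of 30% and 40% are added to show the trend.
- Spread: "assuming a log standard deviation of 0.60". The log base is not given and the quantity is not named. I take natural logs and treat 0.60 as the within-arm SD of log change.
- Eosinophil effect: not given in SD units. Assumed to be 1.5 to 2.7 within-arm SDs.
- No association between eosinophil change and cough change within either arm.

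**Side check on section 9.1.** The standard error of the difference is 0.60 × √(2/15) = 0.219. A 20% effect is −ln(0.80) = 0.223, so two-sided power is Φ(0.223/0.219 − 1.960) = Φ(−0.94), or about 17%, not the stated 80%. With these inputs, 80% power needs a log difference of (1.960 + 0.842) × 0.219 = 0.614, a reduction of 1 − exp(−0.614) = 46%. That is a separate matter and does not affect this point, but it shows that effects well above 20% are the ones this trial could detect.

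**Step 1: cough effect in SDs.** dC = −ln(1 − reduction)/0.60:
- 20%: 0.223/0.60 = 0.372
- 30%: 0.357/0.60 = 0.594
- 40%: 0.511/0.60 = 0.851

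**Step 2: expected pooled correlation.** With two equal arms and no within-arm association,

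r = (dC × dE/4) / √[(1 + dC²/4)(1 + dE²/4)]

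- 20%, dE = 1.5: 0.1395/√(1.0346 × 1.5625) = 0.1395/1.271 = 0.11
- 20%, dE = 2.7: 0.251/√(1.0346 × 2.8225) = 0.251/1.709 = 0.15
- 40%, dE = 1.5: 0.319/√(1.1812 × 1.5625) = 0.319/1.359 = 0.24 (0.235 before rounding)
- 40%, dE = 2.7: 0.575/√(1.1812 × 2.8225) = 0.575/1.826 = 0.31 (0.32 as the simulated mean)

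**Step 3: how often p<0.05.** Simulated trials with 15 per arm, Pearson correlation, two-sided test:

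| Cough effect | Pooled r, dE 1.5 to 2.7 | Pooled p<0.05 | Arm-adjusted p<0.05 |
|---|---|---|---|
| none | 0.00 | 5% | 5% |
| 20% | 0.11 to 0.15 | 9% to 12% | 5% |
| 30% | 0.17 to 0.23 | 15% to 24% | 5% |
| 40% | 0.24 to 0.32 | about 25% to 43% | 5% |

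Widening the assumed eosinophil shift to 1 to 3 SD gives 7% to 13% at a 20% effect, and 19% to 59% at a 46% effect.

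**Step 4: what adjustment costs if the hypothesis is true.** Suppose eosinophil change explains the whole cough effect, linearly and without measurement error, with the same within-arm SDs. The within-arm correlation is then dC/dE. At a 40% effect and a 2.7 SD shift it is 0.851/2.7 = 0.315. Simulation gives p<0.05 in 39% of trials for the arm-adjusted estimate and 82% for the pooled one. A Fisher-z check of the adjusted figure gives 0.326 × √26 − 1.960 = −0.30, or about 38%. At a 20% effect the figures are about 11% to 26% adjusted and 24% to 39% pooled.

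**The case against.** The strongest reply has four parts.

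**Silence is not a choice.** A reader might infer that the sponsor has decided to pool the arms. The document does not say so: it says only that changes will be correlated. Pooling is the plainest reading, but it remains a reading. This part stands.

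**Some tempting premises have no source.** A reader might suppose that eosinophils fall in nearly every treated participant, so that eosinophil change is almost a label for arm. Section 1.2 states a reduction and no more. A reader might also suppose that unblinding creates the cough difference. Section 4's Table 1 counterpart in 5.11 does schedule blood counts after dosing, and section 5.13 does not mention masking them, but sections 5.13 and 6.1 specify double blinding with identical-looking syringes, and nothing shows that the blind would fail. The point needs neither premise: a genuine drug effect on both variables is enough.

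**The size is modest at the planned effect.** At 20% the false-positive rate is 9% to 12%. The 43% figure needs a 40% cough effect, a 2.7 SD eosinophil shift and exactly zero within-arm association together. This also stands.

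**The remedy has a real cost.** Adjusting for arm removes the eosinophil variation that randomisation creates and leaves between-patient scatter. Step 4 shows the loss. A reader might conclude that the pooled correlation is worthless and the adjusted one is the proper test. The documents and the arithmetic do not support that: when eosinophils do mediate the effect, the pooled estimate is the more sensitive of the two. Neither is adequate alone.

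The same sentence also covers patient-reported outcomes. Those correlations mainly ask whether symptoms track cough counts, and the calculation above was not made for them, so the argument should not simply be carried over.

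**Conclusion.** The point holds in a limited form. Section 9.2.3 does not mention arm, and on the plain reading a between-arm difference in cough will appear as a correlation between eosinophils and cough. The direction of this artefact follows from arithmetic whenever the drug lowers both. Its size rests on the assumed eosinophil shift and on taking 0.60 as the SD of natural-log change: small at the planned 20% effect, material at 40% or more, and absent if the drug does not affect cough.

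A significant pooled correlation alone therefore should not be read as evidence that eosinophils drive cough. It would equally be wrong to treat a null arm-adjusted result as refuting the hypothesis, or a positive one as proving causation. The primary comparison and the between-arm comparisons of eosinophils are unaffected. This is a worthwhile clarification of a secondary analysis in a 30-person proof-of-concept trial, not a defect that must be cured.

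**What to change.** In section 9.2.3:
- Add a partial correlation, or a regression of log cough change on eosinophil change, with arm as a covariate.
- Show the estimate within each arm with a confidence interval.
- Report the pooled correlation beside these.
- State the coefficient, scale and time point.
- Say that a significant pooled correlation alone will not be taken as evidence that eosinophils drive cough.

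Arm-adjusted estimates for the patient-reported outcomes are optional.

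The cost is a few lines of text, one degree of freedom, and the loss of power shown in step 4. By Fisher z, power for a true within-arm r of 0.5 is about 80% arm-adjusted with 30 participants (0.549 × √26 − 1.960 = 0.84) and about 48% in one arm of 15 (0.549 × √12 − 1.960 = −0.06), so the emphasis should be on estimates and intervals. Section 9.4 requires an amendment for departures from the statistical plan, so the wording is best settled before unblinding.

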### **9.3. Missing, Unused, Spurious Data**

Spurious data will be re-analyzed with analysis of the primary efficacy endpoints using the primary efficacy analysis set, excluding any spurious data. If the results of this sensitivity analyses confirmed that these participants were influential to the primary endpoint point estimates and treatment effect estimates, the primary efficacy analysis set might be amended to exclude these participants and all endpoints evaluated in this revised analysis set for conclusion purposes.

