### **5.13. Blinding and Randomization**

Subjects will be assigned to one of the two possible treatment arms generated by a computer-generated randomisation schedule prepared by McMaster University, with a ratio of 1:1, mepolizumab or placebo. As there is a known imbalance in the prevalence and cough rates, the study will include sex as a randomisation factor. This will mitigate the possibility of the intervention being confounded by sex differences in the 2 arms of the study. Blinded study drug supplies will be provided in sequentially numbered identical syringes in accordance with the randomisation schedule and dispensed by a pharmacist who shall not be delegated any other role in the study. Subjects, investigators, research staff (with the exception of the pharmacist) and the sponsor will be masked to the treatment sequence assignment. A sealed code-break envelope for each subject containing details of the treatment allocated will be kept in a locked safe at the study site.

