## 9.2. Statistical Analysis

### 9.2.1. General Considerations, Assumptions, and Definitions

This study will generate data of demographics, LCQ scores, modified Borg scores for sensations and cough, methacholine (PC20), blood eosinophils, sputum eosinophil, total and activated mature eosinophils in sputum and blood. These continuous variables will be presented and analysed as either mean (S.D), median (IQR) or geometric mean (geometric S.D). It is generally assumed that cough frequency data will not be normally distributed, and hence cough frequency data will be log transformed and shown as geometric mean (geometric S.D). Statistical significance will be set at  $p<0.05$ .

For the purposes of analysis, the populations for analyses will be defined as:

1. Full analysis set (FAS): consists of all subjects randomized to a treatment arm, who received at least one dose of investigational product irrespective of their protocol adherence and performed at least one period of 24-hr cough monitoring before and one after treatment.
2. Per Protocol Set (PPS): consists of all patients in who did not have any major protocol deviations, and provided cough frequency recording at baseline, 4 weeks and 8 weeks after treatment.

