#### *9.2.2. Primary Endpoint*

The primary endpoint in this study will be the change from baseline in 24-hour cough frequency (geometric mean) after 14 weeks of intervention over placebo (day 98, visit 8) adjusted for baseline cough frequency (day 13, visit 2). The primary efficacy endpoint will be analysed using a generalised estimating equation modelling (GEE) analysis including the baseline cough frequency as a co-variate. Both FAS and PPS populations will be analysed.

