### **9.4. Statistical Plan Deviations**

Any deviations from the original statistical plan would require a protocol amendment and would be described in the final study report.

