### **13.7. Protocol Deviations**

Protocol deviations and/or violations and the reasons they occurred will be included in the clinical study report. Reporting of protocol deviations to the REB and in accordance with applicable regulatory authority mandates is an investigator responsibility. All protocol deviations will be identified, evaluated, and closed before the respective database lock (final analysis) and will be described in the clinical study report. Protocol deviations incurred as a direct result of the COVID-19 pandemic should be specifically recorded as a “COVID-19” deviation so that they can be easily identified and incorporated into the clinical study report.

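### Section 9.3 lets participants with undefined spurious data be removed from the primary set, at discretion, once their influence on the treatment effect is known, and rests all conclusions on that set

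*Combined protocol and SAP*

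**What the plan says.** Section 9.3 has three steps.

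- Re-analysis: "Spurious data will be re-analyzed with analysis of the primary efficacy endpoints using the primary efficacy analysis set, excluding any spurious data".
- Trigger: "If the results of this sensitivity analyses confirmed that these participants were influential to the primary endpoint point estimates and treatment effect estimates".
- Action: "the primary efficacy analysis set might be amended to exclude these participants and all endpoints evaluated in this revised analysis set for conclusion purposes".

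Section 9.2.1 defines two populations. The FAS "consists of all subjects randomized to a treatment arm, who received at least one dose of investigational product irrespective of their protocol adherence", with cough monitoring before and after treatment. The PPS is limited to those without major deviations who have specified recordings. Section 9.2.2 adds: "Both FAS and PPS populations will be analysed". Neither is called primary, and the term used in Section 9.3, the primary efficacy analysis set, is not linked to either.

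Four other provisions come close to this decision:

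- Section 9.4: "Any deviations from the original statistical plan would require a protocol amendment".
- Section 13.7 has protocol deviations settled before the database is locked.
- Section 5.13: "Subjects, investigators, research staff (with the exception of the pharmacist) and the sponsor will be masked to the treatment sequence assignment". Section 6.1 likewise keeps staff and subjects blind during the study.
- Section 5.10.2 (Visits 3, 6 and 9) allows a cough recording to be repeated after device malfunction, and at Visit 6 also for poor quality.

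**The concern.** A sensitivity analysis should show how far the conclusion depends on doubtful data. Here it can replace the analysis that it was meant to test. What prompts the replacement is the effect on the result, not evidence that the data are invalid, and the word chosen for the action leaves it optional.

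The unit also changes: the re-analysis removes data, while the amended set removes whole participants, on every endpoint.

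With 30 participants, a few removals can move the estimate. Section 9.1 says that the data will be used to size later multi-centre studies, so an estimate from a result-dependent set could carry into that planning.

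**Working it through.** **1. Do other sections close the gap?**

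- Section 9.4 governs departures from the plan. Using Section 9.3 is following the plan.
- Section 13.7 sets a pre-lock deadline for protocol deviations, not for spurious data.
- Sections 5.13 and 6.1 mask the study but do not say that the Section 9.3 decision is taken while masked.
- Section 5.10.2 provides repeat recordings but does not define spurious data.

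None of them supplies a definition, a threshold, a decision-maker or a time.

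**2. Inputs.** From the plan: 15 per arm and log SD 0.60 (Section 9.1), significance at 0.05 (Section 9.2.1), baseline cough frequency as covariate (Section 9.2.2). Assumed, because the plan is silent: baseline correlation 0.5, 0.6 or 0.7; normal or variance-scaled t(4) errors; k = 1, 2 or 3 of 30 flagged, either at random or as the largest residuals without regard to arm; influence threshold c = 0.2, 0.37, 0.5 or 1.0 standard errors.

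**3. Model.** Log week-14 rate = a + b × log baseline rate + τ × arm + error, with τ = 0 and a two-sided t-test of τ. This stands in for the planned GEE. Let p0 come from all 30 and p1 from the 30 − k left after the flagged group is dropped. The group is influential if the estimate of τ shifts by more than c × SE. The value 0.37 is 2/√30 = 2/5.477.

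To give that threshold a scale: at correlation 0.6, and reading 0.60 as a natural-log SD of the week-14 rate, the residual SD is 0.60 × √(1 − 0.36) = 0.48. The SE is about 0.48 × √(2/15) = 0.175, and 0.37 × 0.175 = 0.065, a shift of about 6% in the ratio.

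**4. Decision rules.**

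- No exclusion: reject if p0 < 0.05.
- Always dropped: reject if p1 < 0.05.
- Automatic: use p1 if the group is influential, otherwise p0.
- Opportunistic: reject if p0 < 0.05, or if the group is influential and p1 < 0.05.

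**5. Results.** Each setting used 40,000 null trials; the Monte Carlo SE is √(0.05 × 0.95/40,000) = 0.0011, about 0.1 percentage point. The first row checks the plan's nominal 5%, which is recovered.

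| Rule | Random flags | Outlier flags |
|---|---|---|
| No exclusion | 4.4-5.3% | 4.4-5.3% |
| Flagged always dropped | 4.5-5.3% | 4.5-5.3% |
| Automatic, 0.37 SE | 4.7-6.0% | 3.1-5.7% |
| Opportunistic, 0.2 SE | 5.2-6.8% | 6.5-7.7% |
| Opportunistic, 0.37 SE | 4.8-6.5% | 5.9-7.3% |
| Opportunistic, 0.5 SE | 4.7-6.2% | 5.7-7.0% |
| Opportunistic, 1.0 SE | 4.5-5.3% | 4.7-5.6% |

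The largest excess over 5% is 7.7 − 5.0 = 2.7 points at 0.2 SE and 7.3 − 5.0 = 2.3 points at 0.37 SE. Exclusion by a fixed rule adds essentially nothing; the excess comes from letting the result decide.

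**6. How often the choice matters (0.37 SE).** With a true 20% reduction, the choice is open and the two sets disagree on significance in 0.7-4.6% of trials (random flags) or 7.5-18.7% (outlier flags). With no true effect, always keeping the set with the larger reduction gives a mean apparent reduction of 0.1-1.5% or 2.8-5.2%. Both used 20,000 trials per setting.

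**The case against.** The strongest reply is that Section 9.3 says nothing about choosing by p-value. It names influence as the trigger and then moves to the revised set. Applied automatically, that gives error rates at or below nominal in many settings. This stands: a reader might infer that the rule as written produces 5.9-7.3%, but that range assumes an analyst who takes whichever set is significant.

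Three stronger readings also go too far.

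- **The plan prescribes an unblinded choice.** It does not. Estimating an effect requires the arms to be separated, but they could be under coded labels. The plan is silent, so it permits an unblinded choice without stating one.
- **Participants can be hand-picked.** If three were chosen unblinded because they weaken the mepolizumab effect, false positives in its favour would reach 22.6% against 2.5% nominal (normal data, unadjusted t-test). Section 9.3 reaches only participants with data called spurious, so this is an outer bound that the text does not support as an expectation.
- **The FAS and PPS results disappear.** Section 9.2.2 still has both analysed. What is missing is any requirement that conclusions stay with them or that they stand beside the revised result.

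It can also be said that an amended set implies a formal amendment under Section 9.4 or 13.6. The text does not say so, and an amendment made after the effect is known would not remove the dependence on the result.

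Some mitigation stands. Repeat recordings should replace many technical failures before analysis, and this is a proof-of-concept study. The simulation does not use the planned GEE; uncorrected robust errors alone give 6.9-7.9% with no exclusion, which is a separate issue that this fix does not cure.

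**Conclusion.** The point holds as a fault in a stated rule, not as a missing detail: the basis for conclusions on every endpoint can be changed, at discretion, after its effect on the answer is known. The cost in type I error ranges from none to about 2-3 percentage points. The upper end needs opportunistic use, flagged participants who are outliers and a low influence threshold; at 1.0 SE the excess nearly vanishes. All sizes rest on the assumed flagging rate, flagging mechanism and threshold. The rule should be fixed because the remedy is cheap, not because the expected damage is large.

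**What to change.** 1. Delete the provision that lets the primary set be amended for conclusion purposes.
2. Name the FAS as the primary efficacy analysis set and the fixed basis for conclusions on all endpoints.
3. Define an invalid recording by objective technical criteria, applied after the repeat-recording steps of Section 5.10.2 and never by how extreme the value is. Make the judgement masked and before database lock, alongside the Section 13.7 deviation review.
4. Treat only the invalid recording as missing. Keep the participant's other valid post-baseline recording (week 8 or week 14) in the repeated-measures model. State that a participant with no valid baseline recording falls outside the FAS as Section 9.2.1 defines it. Section 9.3 has missing data in its title but gives no method, so this needs to be written down.
5. Report any analysis that excludes spurious or influential participants only as a sensitivity analysis beside the FAS result.
6. Use the PPS as supportive only once its definition is reconciled with the schedule. Section 9.2.1 requires recordings at 4 and 8 weeks, while Section 5.11 C and Table 1 place monitoring at baseline, week 8 and week 14.

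The cost is analysis-plan wording and a short masked check added to an existing review, with no change to visits or procedures. The downside is that an odd but technically valid value stays in the primary analysis.
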